#### Ischemic – reperfusion injury analysis (TnI level 1st day after CABG)

Hypothesis: TnI level 1st after CABG depends on length of operation, length of cardiopulmonary bypass, MPO level before procedure and just after suture performing

Method of hypothesis testing: ANCOVA

ANCOVA model:  $LGTnI1 = LGMPOPostOp LGMPOPreOp CPBTYPE LGMPOPreOp*CPBTYPE AoClamp CPBTime AoClamp*CPBTime OpTime CPBTime* OpTime AoClamp*OpTime$

*Table 11 Variables descriptions*

Variable	Description	Note
TnI1	Troponin I level 1 st day after procedure	Continuous variable
LGMPOPostOp	Logarithm of MPO level during CABG (after suture performing)	Log – transformation for normal distribution
LGMPOPreOp	Logarithm of MPO level before CABG (after suture performing)	Log – transformation for normal distribution
CPBTYPE	Group of intervention	1 – off-pump CABG 2 – on – pump CABG 3 – pump-assisted CABG
AoClamp	Length of aortic cross-clamping, min	Continuous variable
CPBTime	Length of cardiopulmonary bypass, min	Continuous variable
OpTime	Length of procedure, min	Continuous variable
*	Interaction effect	

*Table 12 Characteristics of model*

Source	Sum of Squares	df	Mean Square	F	p	Eta Square

Assessment of Myocardial Ischemic-Reperfusion Injury During Off- and On- Pump CABG (ClinicalTrials.gov Identifier: NCT03050489). Corresponding author: [name] [[contact]](mailto:[contact]) [contact]

Date of the document 06 December 2016

Model	249.3	14	17.8	10.4	0.0001	0.44
-------	-------	----	------	------	--------	------

*Table 13 General linear model characteristics*  $LGTnI1 = LGMPOPostOp LGMPOPreOp CPBTYPE$   
 $LGMPOPreOp*CPBTYPE AoClamp CPBTime AoClamp*CPBTime OpTime CPBTime* OpTime$   
 $AoClamp*OpTime$

Source	Sum of Squares (Type III)	df	Mean Square	F	p	Partial Eta Squared
LGMPOPostOp	2.0	1	2.6	1.2	0.3	0.006
LGMPOPreOp	0.8	1	0.8	0.5	0.5	0.002
AoClamp	2.3	1	2.3	1.4	0.2	0.007
CPBTime	2.2	1	2.2	1.3	0.3	0.007
OpTime	23.3	1	23.3	13.6	0.0003	0.07
CPBType	3.9	2	1.9	1.1	0.3	0.01
CPBTime*OpTime	0.7	1	0.7	0.4	0.5	0.002
AoClamp*CPBTime	0.4	1	0.4	0.22	0.6	0.001
AoClamp*OpTime	3.5	1	3.5	2.1	0.2	0.01
LGMPOPostOp*CPBTYPE	4.1	2	2.1	1.2	0.3	0.01
LGMPOPreOp*CPBTYPE	0.4	2	0.2	0.1	0.9	0.001

**Summary:** troponin I level 1st day postoperatively depends on length of operation

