Title	Assessment of Myocardial Ischemic-Reperfusion Injury During Off- and On- Pump CABG (AMIRI-CABG) ClinicalTrials.gov Identifier: NCT03050489	
Authors *	[name]	
Trial design	Prospective non-randomized single center	
Methods		
Participants	Eligibility criteria: multivessel coronary artery disease with indications for elective coronary artery bypass grafting	
Interventions	Group 1: off-pump CABG Group 2: on-pump CABG Group 3: pump-assisted CABG (on-pump CABG without aortic cross-clamping)	
Objective	To compare level of MPO between three groups of intervention	
Primary objective	To compare ischemic-reperfusion injury between three groups of intervention	

Assessment of Myocardial Ischemic-Reperfusion Injury During Off- and On- Pump CABG  
 (ClinicalTrials.gov Identifier: NCT03050489). Corresponding author: [name]  
[[contact]](mailto:[contact]) [contact]

Date of the document 06 December 2016

Secondary objective	To assess ability of MPO to predict worse outcome (death) To assess relation between MPO and TnI	
Outcome	MPO level after CABG, death after CABG	
Randomization	Non-randomized allocation. Heart Team decision.	
Blinding (masking)	None	
Results		
Numbers randomized	Number of participants screened n=500  Allocated (non-randomized): off-pump CABG (n=181), on-pump CABG (n=128), pump-assisted CABG (n=27)	
Recruitment	Complete	
Numbers analyzed	Off-pump CABG: 181 On-pump CABG: 128 Pump-assisted CABG: 27	
Outcome	Could MPO predict death during 30 days after CABG	
Harms	Important adverse events or side effects	
Conclusions	CPB activates leucocytes that cause myocardial damage  Preoperative MPO level could evaluated as a predictor of myocardial damage and worse outcome after CABG	
Trial registration	ClinicalTrials.gov Identifier: NCT03050489	
Funding	Assessment of regenerative ability after cardiac surgery	

*Table 2 Statistical analysis synopsis*

Assessment of Myocardial Ischemic-Reperfusion Injury During Off- and On- Pump CABG ClinicalTrials.gov Identifier: NCT03050489	
Hypothesis	Ischemic – reperfusion injury are comparable between groups
Primary objective	To compare ischemic-reperfusion injury during off-pump, on-pump and pump – assisted CABG
Secondary objective	To assess ability of myeloperoxidase to predict worse outcome after CABG

Assessment of Myocardial Ischemic-Reperfusion Injury During Off- and On- Pump CABG  
 (ClinicalTrials.gov Identifier: NCT03050489). Corresponding author: [name]  

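### The reported all-patient TnI model (14 df) is not the stated one (12 df), and its two MPO rows test unweighted mean slopes in which about 9 pump-assisted patients carry one third of the weight

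*Combined protocol and SAP*

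**What the plan says.** Table 1 lists among the secondary objectives "To assess relation between MPO and TnI". The section on TnI on day 1 after CABG, which covers all patients, gives the model as "LGTnI1 = LGMPOPostOp LGMPOPreOp CPBTYPE LGMPOPreOp*CPBTYPE AoClamp CPBTime AoClamp*CPBTime OpTime CPBTime* OpTime AoClamp*OpTime", and the title of Table 13 repeats it. The pre-operative MPO by group interaction is in that formula; a post-operative one is not.

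The results in the same section read:

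- Table 12: "Model 249.3 14 17.8 10.4 0.0001 0.44"
- Table 13, interactions: "LGMPOPostOp*CPBTYPE 4.1 2 2.1 1.2 0.3 0.01" and "LGMPOPreOp*CPBTYPE 0.4 2 0.2 0.1 0.9 0.001"
- Table 13, MPO rows: "LGMPOPostOp 2.0 1 2.6 1.2 0.3 0.006" and "LGMPOPreOp 0.8 1 0.8 0.5 0.5 0.002"

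Table 13 labels its sums of squares Type III. The section's summary names only length of operation as a determinant of TnI. The next three sections fit MPO–TnI models separately in on-pump, off-pump and pump-assisted patients.

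**The concern.** The model behind Tables 12 and 13 contains a term, "LGMPOPostOp*CPBTYPE", that the stated formula does not. This changes the question that the post-operative MPO row answers. Beside a covariate-by-class interaction, a Type III covariate row no longer tests one pooled slope. It tests the simple average of the group slopes, however few patients a group has. The pre-operative row has the same property, but there the cause is the interaction that the formula does include.

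These two rows are the only all-patient tests of the MPO–TnI relation. If read as the pooled relation, they give a far less precise answer than about 200 patients could. The results also look inconsistent as they stand. Pre-operative MPO has p=0.5 in all patients but p=0.04 on-pump (Table 16) and p=0.1 off-pump (Table 19), and the conclusions in Table 1 put pre-operative MPO forward as a candidate predictor of myocardial damage.

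**Working it through.** **1. Model df.** The stated formula has PostOp 1, PreOp 1, CPBTYPE 2, PreOp×CPBTYPE 2, three times 3 and three time interactions 3, which total 12. The printed 14 is reached only by adding PostOp×CPBTYPE (2). The row df in Table 13 also sum to 14: 1+1+1+1+1+2+1+1+1+2+2.

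**2. What the MPO rows test.** CPBTYPE has 2 df, so it was a class variable. Under the usual Type III hypotheses (Table 26 refers to SAS code), each MPO row tests (b1+b2+b3)/3. A numerical check on simulated data, comparing the row's estimate with the mean of three separately estimated slopes, gave identical values.

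**3. Patients per group.** The documents do not give the numbers in these models, so they are back-calculated: error df = F × df × (1−η²)/η², and n = error df + df + 1.

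| Model | F, df, η² | Error df | n (range from rounding) |
|---|---|---|---|
| All (Table 12) | 10.4, 14, 0.44 | 185.3 | 200 (196–205) |
| On-pump (Table 15) | 5.4, 8, 0.4 | 64.8 | 74 (61–90) |
| Off-pump (Table 18) | 7.0, 3, 0.15 | 119.0 | 123 (118–129) |
| Pump-assisted (Table 21) | 0.8, 4, 0.45 | 3.9 | 9 (8.6–9.2) |

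The all-patient residual mean square is 249.3/14/10.4 = 1.71.

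**4. Loss of precision.** Let I be a group's information on the slope, proportional to n × (log-MPO SD)². Then Var(unweighted mean)/Var(common slope) = (1/9) × Σ(1/I) × ΣI.

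- Equal spreads: (1/9)(1/123 + 1/74 + 1/9) × 206 = 3.04, an SE ratio of 1.74. The pump-assisted group has weight 0.33, against 9/206 = 0.04 by number, and supplies 84% of the variance.
- Spreads from the Table 7 quartiles, assuming log-normality, SD = ln(Q3/Q1)/1.349. Post-operative SDs are 0.88, 0.46 and 0.81 (off-pump, on-pump, pump-assisted), giving an SE ratio of 1.78. Pre-operative SDs are 0.65, 0.70 and 0.44, giving 2.48.
- Check on the back-calculated 9: Table 25 shows 14 pump-assisted patients with a post-operative MPO value. With 14, (1/9)(1/123 + 1/74 + 1/14) × 211 = 2.18, an SE ratio of 1.48.

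As an illustration only, a slope that a common-slope test would detect with 80% power (two-sided 0.05) would be detected with power Φ(2.80/1.74 − 1.96) = 36%, or 20% at a ratio of 2.48. The plan states no alpha, power or effect size.

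**5. Would a common slope change the result?** The sum of the group-specific SS equals the pooled SS plus the heterogeneity SS, approximately.

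- Pre-operative MPO: 3.9 (on-pump) + 4.9 (off-pump) − 0.4 (interaction) = 8.4; F = 8.4/1.71 = 4.9 on 1 and about 185 df; p about 0.03, against the printed F 0.5, p 0.5. The two larger groups' slopes very probably share a sign: with the quartile-based spreads, opposite signs would imply a heterogeneity SS of about 8.6, not 0.4.
- Post-operative MPO: the group SS are 1.3 on-pump (p=0.2) and 0.1 off-pump (p=0.8). Pooling them gives F 0.01 to 0.30, depending on relative sign. The ceiling for these two groups is 1.4/1.71 = 0.82 (p=0.37). Crediting the whole pump-assisted model SS of 3.7 to post-operative MPO gives 5.1/1.71 = 2.98 (p=0.086).

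**6. Dropping only the extra term** does not cure the pre-operative row. In a simulation with assumed distributions its SE fell from about 0.48 to 0.44; without the pre-operative interaction it was about 0.15.

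**The case against.** The strongest reply has four parts.

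- **The term may simply have been left out of the printed formula.** The document already contains results and shows the term openly in Table 13. Formulas elsewhere in it are loose: the on-pump section repeats the all-patient formula, with its group terms, for a single-group model with 8 df. This stands. A reader might infer an unplanned, data-driven addition, but the documents cannot separate that from an omission. The mismatch needs correcting either way.
- **No relation has been shown to be hidden by the extra term.** A reader might infer that it conceals an MPO–TnI relation. It affects only the post-operative row, where both larger groups show nothing and a common slope would probably give an F below the printed 1.2. Any masking concerns pre-operative MPO and comes from the interaction that is in the formula. This stands.
- **The information was not thrown away.** Each group has its own MPO–TnI model, the on-pump summary reports the pre-operative association, and the all-patient summary does not say that MPO has no effect. This also stands. The all-patient test is still the imprecise one.
- **Removing a written interaction after seeing p=0.9 is itself driven by results,** and with about 9 patients in one group a null interaction is weak evidence of equal slopes. This is fair. It is a reason to label the common-slope analysis as post hoc and to show group-specific slopes beside it, not a reason to leave the rows unexplained.

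**Conclusion.** The point holds in this form. That the reported model differs from the stated one (14 against 12 df) is certain from the printed tables. That both MPO rows are unweighted mean slopes follows from Type III sums of squares with a class variable. Their SE is about 1.7 times that of a common slope at equal spreads, and about 1.7 to 2.5 times across the spreads considered. This rests on back-calculated group sizes, a common residual variance and no allowance for covariate adjustment; with the 14 pump-assisted patients in Table 25 it would be about 1.5.

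The possible change in the pre-operative result (p about 0.03 against 0.5) is a signal, not a finding. The subgroup models use different covariates and have different residual mean squares (0.92 on-pump, 2.08 off-pump, 1.16 pump-assisted, against 1.71 overall). For post-operative MPO the gain is an interpretable slope and interval, probably not a different conclusion.

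This is a should-fix. The study is declared exploratory, and the primary Kruskal-Wallis comparison of MPO is untouched.

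**What to change.** 1. Reconcile the formula and the Table 13 title with Tables 12 and 13, and say whether the post-operative interaction was intended. Correct the post-operative MPO row, which prints SS 2.0 but mean square 2.6 on 1 df; F 1.2 fits 2.0.
2. State under Table 13 that the two printed MPO rows test unweighted means of the three group slopes.
3. Report common pre-operative and post-operative MPO slopes with 95% confidence intervals from a model without either MPO-by-group term, labelled as added after the results were seen. Give the group-specific slopes with intervals beside them.
4. Present the two interaction tests (p=0.3 and 0.9) only as checks on heterogeneity, and note their low power with about 9 pump-assisted patients.
5. Revisit the section's summary in the light of these estimates.

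The cost is one re-run on existing data and some SAP wording. The drawback is that the common-slope result depends on the slopes being similar across groups, which these data can check only weakly for the pump-assisted group.

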#### Ischemic – reperfusion injury analysis (TnI level 1st day after on – pump CABG)

Hypothesis: TnI level 1st day after on-pump CABG depends on length of operation, length of cardiopulmonary bypass, MPO level before procedure and after suture performing

Method of hypothesis testing: ANCOVA

ANCOVA model:  $LGTnI1 = LGMPOPostOp LGMPOPreOp CPBTYPE LGMPOPreOp*CPBTYPE$   
 $AoClamp CPBTime AoClamp*CPBTime OpTime CPBTime* OpTime AoClamp*OpTime$

*Table 14 Variables description*

Variable	Description	Note
TnI1	Troponin I level 1 st day after procedure	Continuous variable
LGMPOPostOp	Logarithm of MPO level during CABG (after suture performing)	Log – transformation for normal distribution
LGMPOPreOp	Logarithm of MPO level before CABG (after suture performing)	Log – transformation for normal distribution
CPBTYPE	Group of intervention	1 – off-pump CABG 2 – on – pump CABG 3 – pump-assisted CABG
AoClamp	Length of aortic cross-clamping, min	Continuous variable
CPBTime	Length of cardiopulmonary bypass, min	Continuous variable
OpTime	Length of procedure, min	Continuous variable
*	Interaction effect	

Assessment of Myocardial Ischemic-Reperfusion Injury During Off- and On- Pump CABG (ClinicalTrials.gov Identifier: NCT03050489). Corresponding author: [name] [[contact]](mailto:[contact]) [contact]

Date of the document 06 December 2016

*Table 15 Characteristics of model*

Source	Sum of Squares	df	Mean Square	F	p	Eta Square
Model	39.7	8	4.96	5.4	0.0001	0.4

*Table 16 Characteristics of model LGTnI1 = LGMPOPostOp LGMPOPreOp CPBTYPE*

*LGMPOPreOp\*CPBTYPE AoClamp CPBTime AoClamp\*CPBTime OpTime CPBTime\* OpTime AoClamp\*OpTime*

Source	Sum of Squares (Type III)	df	Mean Square	F	p	Partial Eta Squared
LGMPOPostOp	1.3	1	1.3	1.4	0.2	0.02
LGMPOPreOp	3.9	1	3.9	4.2	0.04	0.06
AoClamp	0.9	1	0.9	1.0	0.3	0.02
CPBTime	7.4	1	7.4	8.1	0.006	0.1
OpTime	3.4	1	3.4	3.7	0.06	0.05
CPBTime*OpTime	0.01	1	0.1	0.1	0.8	0.0009
AoClamp*CPBTime	5.5	1	5.5	5.9	0.02	0.08
AoClamp*OpTime	1.6	1	1.6	1.7	0.2	0.026

**Summary:** troponin I level 1st day after on-pump CABG affected by length of cardiopulmonary bypass, preoperative MPO level and interaction of duration of aortic cross clamping and length of cardiopulmonary bypass.

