### **DATA ANALYSIS**

#### **Sample Size Justification**

Since it is exploratory study and no statistical hypotheses will be tested, sample size calculation was not conducted for this study. Thus, about 300 patients is planned to be included in the analysis.

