#### **Ischemic – reperfusion injury analysis (TnI level 1st day after off – pump CABG)**

Hypothesis: TnI level 1st day after off-pump CABG depends on length of operation, MPO level before procedure and after suture performing

Method of hypothesis testing: ANCOVA

ANCOVA model: LGTnI1= LGMPOPostOp LGMPOPreOp OpTime

*Table 17 Variables description*

Variable	Description	Note
TnI1	Troponin I level 1 st day after procedure	Continuous variable
LGMPOPostOp	Logarithm of MPO level during CABG (after suture performing)	Log – transformation for normal distribution
LGMPOPreOp	Logarithm of MPO level before CABG (after suture performing)	Log – transformation for normal distribution
OpTime	Length of procedure, min	Continuous variable

*Table 18 Characteristics of model*

Source	Sum of Squares	df	Mean Square	F	p	Eta Square
Model	43.7	3	14.6	7.0	0.0002	0.15

Assessment of Myocardial Ischemic-Reperfusion Injury During Off- and On- Pump CABG (ClinicalTrials.gov Identifier: NCT03050489). Corresponding author: [name] [[contact]](mailto:[contact]) [contact]

Date of the document 06 December 2016

*Table 19 Characteristics of model LGTnI1= LGMPOPostOp LGMPOPreOp OpTime*

Source	Sum of Squares (Type III)	df	Mean Square	F	p	Partial Eta Squared
LGMPOPostOp	0.1	1	0.1	0.06	0.8	0.0005
LGMPOPreOp	4.9	1	4.9	2.36	0.1	0.02
OpTime	38.5	1	38.5	18.58	0.0001	0.1

Summary: troponin I level 1st day after on-pump CABG affected by length of operation.

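### The on-pump troponin summary reads the Table 16 bypass-time row as an effect of bypass time, but with no centring stated that row tests zero clamp and operation time; the off-pump summary names the wrong group

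*Combined protocol and SAP*

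**What the plan says.** In the section on troponin I (TnI) on day 1 after on-pump CABG, log TnI is modelled on MPO before and after suturing, AoClamp, CPBTime, OpTime and the three pairwise products of those times. Table 14 defines the times as "Length of aortic cross-clamping, min", "Length of cardiopulmonary bypass, min" and "Length of procedure, min". Neither the section nor the table mentions centring. Table 15 gives the overall fit as "Model 39.7 8 4.96 5.4 0.0001 0.4", and the bypass row of the Type III table (Table 16) reads "CPBTime 7.4 1 7.4 8.1 0.006 0.1". The summary says TnI is "affected by length of cardiopulmonary bypass, preoperative MPO level and interaction" of clamp and bypass durations. It does not name operation length (p=0.06) or clamp time alone (p=0.3).

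The pooled section just before it fits all three groups with the same time products. It concludes that TnI depends on length of operation (Table 13, OpTime p=0.0003).

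The section just after it has an off-pump heading, hypothesis and model. Table 19 gives OpTime F 18.58, p=0.0001. Its summary nevertheless reads "day after on-pump CABG affected by length of operation".

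**The concern.** When a model contains products of continuous variables, the test of one variable alone is a test of its slope where the variables it is multiplied by equal zero. With times in raw minutes, the CPBTime row describes an on-pump operation that had no clamp time and took no time at all. Moving the origin of the time scales changes that row and its p-value without changing the fit. The document's own interaction (p=0.02) says that the bypass slope varies with clamp time, so where the slope is evaluated matters. The summary gives no slope, direction, interval or reference clamp time.

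The wrong group name adds a contradiction. Two consecutive summaries give different on-pump drivers of TnI, and no off-pump conclusion is stated at all. Comparing TnI between groups is listed under the primary objective, so these summaries are likely to be quoted.

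**Working it through.** **1. Reproduce Table 16.**
- Mean square error = model mean square / F = 4.96 / 5.4 = 0.919.
- Error sum of squares = 39.7 × (1 − 0.4) / 0.4 = 59.55.
- Residual df = 59.55 / 0.919 ≈ 65, so n ≈ 65 + 8 + 1 = 74. Rounding of eta squared (0.35 to 0.45) gives n of about 62 to 89.

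| Row | SS / 0.919 | p on (1, 65) df | Stated |
|---|---|---|---|
| CPBTime | 7.4 → 8.05 | 0.006 | F 8.1, p 0.006 |
| LGMPOPreOp | 3.9 → 4.24 | 0.043 | F 4.2, p 0.04 |
| AoClamp*CPBTime | 5.5 → 5.98 | 0.017 | F 5.9, p 0.02 |
| OpTime | 3.4 → 3.70 | 0.059 | F 3.7, p 0.06 |

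The rows agree with the table. One row does not agree with itself: CPBTime*OpTime has SS 0.01 but mean square 0.1 on 1 df.

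The 8 model df match the 8 rows. The CPBTYPE terms in the written formula therefore dropped out, as they must within one group.

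**2. What the CPBTime row tests.** In this model the bypass slope is b_C + b_AC × AoClamp + b_CO × OpTime. The row tests b_C alone, which is the slope at AoClamp = OpTime = 0. This is algebra and needs no simulation.

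**3. What does not depend on the origin.** Shifting the times leaves the fitted model unchanged. It also leaves unchanged the product coefficients and the preoperative MPO coefficient, which is in no fitted product. Only the AoClamp, CPBTime and OpTime rows move.

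**4. The slope test at typical times.** This needs coefficients, their covariances and the mean times, and the document gives none of them. As an illustration, 74-patient designs were calibrated to the Table 16 F values and kept when the model SS was within 4 of 39.7. The assumed times were mean clamp 35-80 min, bypass 1.3-2 times clamp, and operation 80-180 min longer than bypass. The CPBTime p at the means ran from below 0.0001 to 0.99, with median 0.0009, and was above 0.05 in about 16%. The OpTime p at the means also ran from below 0.0001 to 0.99, and was below 0.05 in about 65%. These shares follow from the assumptions and show only that the results are undetermined.

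**5. A bound that needs no assumed times.** Dropping CPBTime with both its products removes at least as much SS as dropping CPBTime alone, so at least 7.4. Hence the joint F is at least (7.4 / 3) / 0.919 ≈ 2.69 on (3, 65) df, and p is at most about 0.054. Over residual df of 53 to 80 the bound is 0.056 to 0.052.

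**6. Pooled model (Tables 12 and 13).**
- Mean square error = 17.8 / 10.4 = 1.71; error SS = 249.3 × 0.56 / 0.44 ≈ 317; residual df ≈ 185; n ≈ 185 + 14 + 1 = 200.
- Postoperative MPO is present for 102 + 14 = 116 on-pump and pump-assisted patients (Table 25). At least about 200 − 116 = 84 off-pump patients are therefore in the model, presumably with clamp and bypass time entered as zero.
- The OpTime row there is the slope at zero clamp and zero bypass time, which describes off-pump patients.

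**7. Whose data are in Table 19.**
- Mean square error = (43.7 / 3) / 7.0 = 2.08; error SS = 43.7 × 0.85 / 0.15 = 247.6; residual df ≈ 119; n ≈ 119 + 3 + 1 = 123, or about 119 to 128 over rounding of eta squared.
- Table 25 has 102 on-pump and 153 off-pump patients with postoperative MPO. An n of 119 or more is impossible for on-pump and possible for off-pump.

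**The case against.** The strongest reply has four parts.

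- **Bypass time may well matter.** A non-zero clamp-by-bypass interaction already means that TnI varies with bypass time at some clamp times, and the joint test has p no worse than about 0.054. This stands. What is missing is the slope at clamp and operation times that patients had. The summary also mentions the interaction in the same sentence, so a careful reader is warned that the effect is not uniform.
- **Centring is not ruled out.** That the times were uncentred is inferred from the minute units and from silence. If they were centred, a sentence saying so settles the main point.
- **The study is exploratory.** It says that "no statistical hypotheses will be tested, sample size calculation was not conducted for this study", and this is a one-group subanalysis. That lowers the stakes. It does not make a slope at impossible times an answer to the question, and the summary still states a conclusion.
- **The group name is a slip.** Agreed: heading, hypothesis, model and implied n are all off-pump.

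A reader might go further than the document allows. All three on-pump conclusions do not fall, since two of them are independent of the origin. The summary does not misread the AoClamp and OpTime rows, because it claims no effect of either. The operation-length result is not without a table: Table 19 shows it clearly, for off-pump. Nor does centring at on-pump means carry over to the pooled Table 13, where zero clamp and bypass time is the real value for off-pump patients, apart from any of the 6 conversions.

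**Conclusion.** The point holds in limited form. If the times were entered uncentred, as the tables suggest, p=0.006 for CPBTime answers a question about patients who do not exist. The bypass-time part of the on-pump summary is then not supported at typical times. This does not show that bypass time has no effect: the p-value at typical times is unknown and could be smaller or larger. Likewise the on-pump OpTime p of 0.06 is conditional on zero clamp and bypass time, so it should not be cited as evidence of no operation-length effect.

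The pooled OpTime result is interpretable, but as an off-pump slope and not as a statement about all CABG. This assumes that off-pump times were entered as zero.

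The group name in the off-pump summary is wrong. That conclusion rests on the section's own text and on the implied n of about 119-128 against 102, and needs no assumed times.

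**What to change.** 1. **On-pump model.** Centre the three times at their on-pump means and refit, or state that they were already centred. Report the bypass slope with 95% CI at the mean and quartiles of clamp time. Add the 3-df joint test of CPBTime with its two products. Reword only the bypass part of the summary from these results.
2. **Pooled model.** Keep the Table 13 OpTime row but label it as the slope at zero clamp and bypass time. Report OpTime slopes at typical on-pump times separately.
3. **Off-pump summary.** Change on-pump to off-pump.
4. **Tidying.** Remove the CPBTYPE terms from the single-group on-pump formula and reconcile the SS and mean square in the CPBTime*OpTime row.

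The cost is a rerun of two existing models and some rewording. No new data are needed.

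### The claim that pre-operative MPO affects day-1 troponin rests on a row that holds post-suture MPO and operating times fixed; no model tests pre-operative MPO as a predictor of myocardial damage

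*Combined protocol and SAP*

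**What the plan says.** In the section on TnI level 1st day after on-pump CABG, the MPO and group part of the model is "LGTnI1 = LGMPOPostOp LGMPOPreOp CPBTYPE LGMPOPreOp*CPBTYPE" and the time part is "AoClamp CPBTime AoClamp*CPBTime OpTime CPBTime* OpTime AoClamp*OpTime". The group variable is constant among on-pump patients, so eight one-degree-of-freedom rows remain, as Tables 15 and 16 show. The Table 16 column is headed "Sum of Squares (Type III", so each row is adjusted for the other seven. The pre-operative MPO row reads "LGMPOPreOp 3.9 1 3.9 4.2 0.04 0.06". The Summary then states that troponin is "affected by length of cardiopulmonary bypass, preoperative MPO level" and an interaction of cross-clamp and bypass time.

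The other three troponin models (pooled, off-pump, pump-assisted) also contain post-suture MPO. The off-pump model, for example, is "LGTnI1= LGMPOPostOp LGMPOPreOp OpTime". The death model uses only the MPO value taken after CABG.

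The Conclusions row of Table 1 says: "Preoperative MPO level could evaluated as a predictor of myocardial damage and worse outcome after CABG".

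**The concern.** The Myeloperoxidase Test section takes the second sample during surgery, right after the coronary suturing. Cross-clamp, bypass and operation times are likewise known only once surgery is under way or over. The section on ischemic-reperfusion injury by MPO level hypothesises that post-suture MPO depends on the pre-operative level, and models it that way. Post-suture MPO is thus a possible step on the path from pre-operative MPO to troponin.

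A predictor of damage has to be judged on what is known before surgery. The Table 16 row instead compares patients who reached the same post-suture MPO with the same operating times. Among them, a higher pre-operative value means a smaller intra-operative rise. That can be a legitimate question, but it is a different one from prediction.

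At stake is the only nominally significant MPO result in the troponin analyses. Elsewhere the pre- and post-suture rows have p of 0.5 and 0.3 (pooled) and 0.1 and 0.8 (off-pump). The pump-assisted model has an overall p of 0.6.

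**Working it through.** **1. Reproducing the printed row (Tables 15 and 16).**
- Model mean square = 39.7/8 = 4.96; error mean square = 4.96/5.4 = 0.919.
- Error sum of squares from eta squared 0.4: 39.7 × 0.6/0.4 = 59.55; error df = 59.55/0.919 ≈ 65; patients ≈ 65 + 8 + 1 = 74. Rounding in the pre-operative row alone allows error df of about 60 to 73.
- Pre-operative MPO: F = 3.9/0.919 = 4.24 (printed 4.2); p from F = 4.2 on 1 and 65 df = 0.0445 (printed 0.04); partial eta squared = 3.9/(3.9 + 59.55) = 0.061 (printed 0.06).

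The row is internally coherent. What it means is a separate matter.

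**2. What the coefficient is.** Let a and b be the slopes of log post-suture and log pre-operative MPO. Then a·post + b·pre = a·(post − pre) + (a + b)·pre. So b is the effect of the pre-operative value at a fixed post-suture value. Without post-suture MPO in the model, the slope is b + a·γ, where γ is the slope of post on pre. None of a, b or γ is printed for the troponin models.

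**3. Dropping post-suture MPO only, same patients.** Inputs: |t_pre| = √4.2 = 2.05 and |t_post| = √1.4 = 1.18. With ρ the pre/post correlation given the times (not printed; assumed 0 to 0.9):

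t* = (t_pre + ρ·t_post)/√(1 − ρ²), divided by √(66.4/66) for the new error mean square.

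| ρ | p, slopes of same sign | p, slopes of opposite sign |
|---|---|---|
| 0 | 0.045 | 0.045 |
| 0.1 | 0.033 | 0.057 |
| 0.3 | 0.014 | 0.081 |
| 0.5 | 0.003 | 0.098 |
| 0.7 | 0.0002 | 0.093 |
| 0.9 | <0.001 | 0.028 |

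The weakest case is ρ ≈ 0.58 with opposite signs: |t| = 1.67, p = 0.10. Because 2.05 exceeds 1.18, the numerator keeps the sign of t_pre for every ρ.

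**4. Dropping post-suture MPO and all time terms, same patients.** Semi-partial correlation = √(3.9/(39.7 + 59.55)) = 0.198; model R² = 0.4. Let c be the correlation of pre-operative MPO with the fitted score of the other seven terms (not printed). As a simplification, assume pre-operative MPO relates to those terms only through that score. Then b = 0.198/√(1 − c²) in standardised form, s solves b² + s² + 2bsc = 0.4, and the marginal correlation is r = b + s·c. Taking the conditional row as positive:
- c = 0: r = 0.20, p = 0.09
- c = 0.2: r = 0.31, p = 0.006
- c = 0.3: r = 0.37, p = 0.001
- c = −0.3: r = 0.01, p = 0.94
- c = −0.6: r = −0.20, p = 0.08

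A sign change needs c below about −0.31.

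**5. Patients available (on-pump column, Tables 7 and 30).** Pre-operative MPO is missing in 21 of 128, post-suture MPO in 26, and day-1 troponin in 10. A model needing only pre-operative MPO and day-1 troponin would use between 128 − 21 − 10 = 97 (missing values in different patients) and 128 − 21 = 107 (complete overlap). The present model uses about 74.

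**The case against.** The model fits its declared hypothesis, which is joint: troponin depends on operation length, bypass length, and MPO before the procedure and after suturing. The study is labelled exploratory, the Table 1 sentence is tentative, and no passage says that it rests on Table 16. The secondary objective in Table 1 on MPO and troponin is to assess their relation; the explicit prediction objective concerns worse outcome (death). This supports keeping the model. It does not support the untentative wording of the Summary, and it does not supply a test of the Table 1 statement.

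The operating times may also serve as precision covariates, since nothing in the documents says that pre-operative MPO influences them. Omitting them has a price. At c = 0, r = 0.20 gives p = 0.09 with 74 patients, 0.052 with 97 and 0.041 with 107. A non-significant simple model would therefore not show that the Table 16 row is wrong. This stands, and it argues for showing both versions.

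A reader might infer that the true relation runs the other way, with higher pre-operative MPO going with less troponin. The documents do not support that. F carries no sign, and neither the Summary nor Table 1 states a direction to be contradicted. If troponin followed only the rise (b = −a), the printed F pattern could arise with a negative row, but b = +a gives nearly the same pattern. In the rise-only case the slope without post-suture MPO is −a(1 − γ). With log SDs from the Table 7 on-pump quartiles (ln(48.7/19.0)/1.349 = 0.698 and ln(250/135)/1.349 = 0.457) and an assumed correlation of 0 to 0.4, γ is 0 to 0.4 × 0.457/0.698 = 0.26. That slope then keeps the sign of b and 74% to 100% of its size. Step 3 shows that removing post-suture MPO cannot reverse the sign in the same patients. A reversal needs the times removed as well, with a fairly strong negative c, or a different patient set.

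**Conclusion.** The concern holds as a gap between model and conclusion. The Table 16 row is a conditional association (partial r about 0.25 in size, from √0.061; sign unprinted) in about 74 of 128 on-pump patients. It does not test what pre-operative MPO predicts before surgery, and neither does any other model in the document. The unconditional association could be weaker or stronger: p from below 0.001 to 0.10 when post-suture MPO alone is dropped, and r from −0.20 to +0.37 when the times are dropped too. Those ranges rest on assumed values of ρ (0 to 0.9) and c (−0.6 to 0.3), on the simplification in step 4, and on the same patients being analysed. They show what the printed figures leave open and do not estimate the answer. There is no evidence of a reversed sign.

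The point is separate from multiplicity. A much smaller p in the same row would still answer the conditional question.

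**What to change.** - For the prediction question, add `LGTnI1 = LGMPOPreOp` in on-pump patients, and a pooled version with `CPBTYPE`, without `LGMPOPostOp`, `AoClamp`, `CPBTime` or `OpTime`. Use every patient with pre-operative MPO and day-1 troponin. Report the signed slope with its 95% CI.
- As a sensitivity analysis, a version that keeps the operating times but drops `LGMPOPostOp` may be shown.
- Keep the present model for its joint hypothesis, print signed slopes with CIs, and describe the pre-operative MPO row as conditional on post-suture MPO and operating times.
- Base the Summary and the Table 1 wording on pre-operative MPO as a predictor of myocardial damage, including any direction, on the pre-operative-only model.

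The cost is one extra model on existing data, some loss of precision from omitting the times, and the chance that the claim does not survive. In return, on-pump patients rise from about 74 to between 97 and 107, and the model no longer requires the post-suture sample, whose gaps the plan's own missing-data section classes as missing not at random. The 21 patients without pre-operative MPO remain excluded, and the report should say so.
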